**Summary of Changes from SAP version 1.0 dated 23 June 2022**

Section, paragraph	Description of Change	Rationale
Cover page	Protocol version and date updated	Per the amended protocol
1	
A sentence is added to clarify that the SAP does not include PK analyses.
 
The sentence “The analysis methods presented in this SAP will supersede the statistical analysis methods described in the clinical protocol” is deleted.
	
Clarification
 
Per FDA

2.2	Items 1 and 4 edited	Per the amended protocol
2.3	Primary Estimand section moved from Section 2.5 to 2.3	Administrative
2.4	Minor edits made to Items 1 and 4, Cognitive assessment added as a safety objective as item 5	Per the amended protocol
2.5	Section Title edited	Per the amended protocol
5.1	Math formula simplified with other minor editions	Administrative
5.2	
Items 1 and 4 re-phrased
 
Math formula simplified with other minor editions
	
Per the amended protocol
 
Administrative

5.3	Minor edit made to item 4	Per the amended protocol
6.2	The last 2 bullet points re-phrased	Per the amended protocol

6.7.1, paragraph 1	The last sentence deleted	Administrative
6.10.1	The last 2 bullet points edited	Per the amended protocol
7.1, paragraphs 1 and 2	Editorial changes	Per the amended protocol
7.3	Editorial change	Per the amended protocol
10	Revised according to the amendment protocol	There is no change in any planned analyses per the amended protocol
11	First reference deleted	Administrative

## LIST OF ABBREVIATIONS

AE	Adverse event
AESI	adverse events of special interest
ANCOVA	analysis of covariance
ATC	Anatomical Therapeutic Chemical
BMI	body mass index
BP	blood pressure
bpm	beats per minute
CFB	change from baseline
CGI-I	Clinical Global Impression – Improvement
CGI-S	Clinical Global Impression – Severity of Illness
CI	confidence intervals
CRF	case report form
CRO	contract research organization
C-SSRS	Columbia Suicide Severity Rating Scale
CSR	clinical study report
DBL	Double-blind
DSM-5	Diagnostic and Statistical Manual of Mental Disorders – 5th Edition
ECG	electrocardiogram
EOS	end of study
ET	early termination
FAS	Full Analysis Set
HRQoL	Health-related quality of life
IC or ICF	informed consent or informed consent form
ICH	International Council for Harmonization
LS	least squares
MAR	missing at random
MedDRA	medical dictionary for regulatory activities
mg	milligram

MI	multiple imputation
MI	Metacognitive Index
MMRM	mixed model with repeated measures
MNAR	missing not at random
ms	millisecond
N	number
NA	not applicable
PP	per protocol
PT	preferred term
QD	once daily
SAE	serious adverse event
SAP	statistical analysis plan
SAS®	a software system used for data analysis
SD	standard deviation
SM	study medication
SOC	system organ class
TEAE	treatment-emergent adverse event
TPM	Topiramate
WHO	World Health Organization
WHO-DDE	World Health Organization Drug Dictionary Enhanced

## 1. Introduction

This statistical analysis plan (SAP) describes the statistical analyses and data presentations to be performed on Study 538P401, protocol version 4.0, dated 14Dec2022.

The purpose of this SAP is to ensure the credibility of the study findings by specifying detailed statistical approaches to the analyses of the data prior to database lock. This SAP covers the planned analyses of all data collected on the eCRFs, headache and other diary pages including externally transferred laboratory data and will describe handling of data issues. It describes the efficacy and safety variables, anticipated data handling, and other details of the analyses not provided in the study protocol. The analysis of pharmacokinetics (PK) data and the population PK modelling are not covered in this SAP. Any deviations/changes from the planned analyses described in this SAP will be identified, with justification, in the appropriate section of the clinical study report.

## 2. Study Objectives

### 2.1. Primary Objective

The primary objective of this study is to evaluate the treatment effect of SPN-538 compared to placebo in reducing monthly migraine days in children 6 to 11 years old with migraine.

### 2.2. Secondary Objectives

The secondary objectives of this study are to assess the efficacy of SPN-538 treatment on the following:

1. Responder rate with a responder defined as a subject with at least a 50% reduction in monthly migraine days (MMDs).
2. Number of days per month requiring acute rescue medication.
3. Monthly rate of total headache days (migraine and non-migraine), duration and severity.
4. Onset of action, defined as the time to first statistically significant treatment effect observed and maintained until the end of the study (EOS).
5. Headache Disability Score as measured by the Pediatric Migraine Disability Assessment (PedMIDAS).
6. Health-related quality of life (HRQoL) as measured by the Pediatric Quality of Life Inventory, Version 4.0 (PedsQL 4.0), for the self-report and parent-report.

### 2.3. Primary Estimand

According to the ICH E9 Addendum, the attributes of the primary estimand (target of estimation) are provided below.

1. Treatment: To compare the treatment effect of SPN-538 vs Placebo.
2. Population: The population targeted for the scientific question is defined via the inclusion and exclusion criteria in children 6 to 11 years old (inclusive) with a history of migraine.

3. Variable: The primary efficacy endpoint is the change from baseline in the monthly (28-day) rate of migraine days during the last 4 weeks of the 20-week double-blind Treatment Phase relative to the Prospective Baseline Period based on the Full Analysis Set (FAS).
4. Intercurrent Events: For subjects discontinued due to adverse event (AE) or lack of efficacy, missing data will be imputed using multiple imputation under the Missing Not at Random (MNAR) assumption. For all other missing data due to Intercurrent events (ICE), missing data will not be imputed following the treatment policy strategy, which assumes that ICE did not occur.
5. Population level summary: The difference in the mean change from baseline in the monthly (28-day) rate of migraine days during the last 4 weeks of the Treatment Phase between the SPN-538 and placebo groups will be analyzed using a Mixed Model for Repeated Measures (MMRM).

#### **2.4. Safety Objective**

To evaluate the safety and tolerability of SPN-538 in children 6 to 11 years old as assessed by:

1. Incidence of AEs.
2. Clinical laboratory tests (blood chemistry and hematology, urinalysis).
3. Vital signs, physical and neurological examinations, and electrocardiograms (ECGs).
4. Columbia Suicide Severity Rating Scale (C-SSRS) Assessment.
5. Cognitive Assessment.

[figure not shown]
### **3. Study Description**

#### **3.1. Study Design**

This is a multicenter, randomized, double-blind, placebo-controlled, 2-arm, parallel group Phase 4 study in children 6 to 11 years of age to evaluate the efficacy and safety of SPN-538 for the prevention of migraine. SPN-538 (or matching placebo) will be administered as a single oral dose once a day (QD), [REDACTED]

[REDACTED] The total study duration is a maximum of 34 weeks, including a Screening/Wash-out Period and Prospective Baseline Period of up to 8 weeks; a Treatment Phase of 20 weeks (8 weeks titration followed by 12 weeks of maintenance dosing); a Dose Tapering Period of 1 to 3 weeks; and a Safety Follow-up period of 1 to 3 weeks. Approximately 35 sites in the United States (US) are planned. The study schematic is shown in Figure 1 and described below

Figure 1 Study Schematic

EOS = end of study; V = visit

2. Subjects will receive a follow-up telephone call 1 to 3 weeks following discontinuation of study medication (Visit 9/EOS or early termination).

Table 2 Schedule of Events and Assessments

Assessments	Pre-treatment Phase		Treatment Phase				Post-treatment Phase	
	Screening/ Washout a	Prospective Baseline	Random- ization	Titration		Maintenance	Taper (EOS) (ET)	Safety Follow up (by phone)
Study Visit #	1	2	3	4	5	6,7	8	9
Day of Study Visit	-56	-28	1	29	57	85,113	141	162
Week of Study Visit	-8 to -5	-4 to -1	-	4b	8b	12,16b	20b	21-23
Study Visit Window	up to 4wks before V2	4wks before V3	+ 2 days	± 7 days	± 7 days	± 7 days	± 7 days	± 7 days
Informed consent/assent	X c							
Demographics	X							
Retrospective 3-months headache history	X							
Randomization			X					
Inclusion/exclusion criteria	X		X					
Medical, family & psychiatric histories	X							
Physical & neurological examinations	X d			X d		X d	X d	
Visual Neurological Exam	X						X	
Placebo Training		X		X m		X [V6] m		
ECG (12-lead)	X			X			X	
Vital signs	X e	X e	X e	X e	X e	X e	X e	
Hematology/Chemistry/ Urinalysis	X	X		X	X	X	X	
Serum pregnancy test	X							

Assessments	Pre-treatment Phase		Treatment Phase				Post-treatment Phase	
	Screening/ Washout a	Prospective Baseline	Random- ization	Titration		Maintenance		Taper (EOS) (ET)
Study Visit #	1	2	3	4	5	6,7	8	9
Day of Study Visit	-56	-28	1	29	57	85,113	141	162
Week of Study Visit	-8 to -5	-4 to -1	-	4 b	8 b	12,16 b	20 b	21-23
Study Visit Window	up to 4wks before V2	4wks before V3	+ 2 days	± 7 days	± 7 days	± 7 days	± 7 days	± 7 days
(FOCP only)								
Urine pregnancy test (FOCP only)		X	X	X	X	X	X	
Urine drug screen	X				X	X	X	
Eye Exam			X			X [V6]		X
C-SSRS	X f	X f	X f	X f	X f	X	X	
Concomitant medications	X f	X f	X f	X f	X f	X f	X f	X f
Review Headache Diary		X g	X g	X g	X g	X g	X g	
PedMIDAS	X		X		X		X	
PedsQL 4.0			X		X		X	
Cognitive assessment			X		X	X	X	
Dispense SM			X h	X	X	X	X i	
AEs			X	X j	X j	X j	X j	X j
SM return & adherence			X	X	X	X	X	

AE = adverse event; C-SSRS = Columbia Suicide Severity Rating Scale; ECG = electrocardiogram; EOS = end of study; ET = early termination visit; FOCP = females of childbearing potential; PedMIDAS = Pediatric Migraine Disability Assessment Questionnaire; PedsQL = Pediatric Quality of Life Inventory; PK = pharmacokinetics; SM = study medication;

- a. Subjects who had used TPM or any prophylactic migraine therapy within 4 weeks prior to Screening must complete a washout period of at least 2 weeks before the start of the Prospective Baseline Period.
- b. Bi-weekly telephone contacts will occur between study visits, at Days 14, 43, 71, 99, and 127 ( $\pm$  2 days).
- c. Informed consent/assent to be obtained prior to performing any study procedures.
- d. Physical examination (excluding genitourinary system) includes height and weight and a special assessment for the occurrence of decreased sweating and elevation in body temperature above normal. Neurological examination includes evaluation for impaired reflexes, balance problems, muscle weakness, paresthesia/numbness and tingling, speech difficulties, mental confusion or excessive fatigue.
- e. Seated (5 min) pulse, blood pressure, temperature and respiratory rate. The vital signs readings, except prior to dosing, will be performed within approximately 10 minutes prior to scheduled blood draws, where applicable.
- f. Concomitant medication includes headache rescue medicine (also recorded in the Headache Diary).
- g. Headache Diary training will be provided at Visit 2.
- h. Subjects will start the first dose on the same day of Visit 3 at the clinical site, instructions for dose titration will be provided.
- i. Provide instructions for dose tapering at Visit 8.
- j. Any subject who experiences an AE (whether serious or non-serious) or has a clinically significant abnormal laboratory test value will be followed by the Investigator for up to 30 days after the EOS visit. These subjects will be treated and/or followed up until the symptoms or value(s) return to normal/baseline or acceptable levels, as determined by the Investigator.

[REDACTED]

- l. Safety Follow Up (by Phone) is not a site visit and falls within a range of 1-3 weeks after Visit 9 occurs.
- m. Placebo training refresher

### **3.2. Study Population**

The study population will comprise of children 6 to 11 years old (inclusive) with a history of migraine with or without aura, conforming to the third edition of the International Classification of Headache Disorders (ICHD-3) by the International Headache Society criteria for pediatric subjects for at least 6 months prior to Screening.

### **3.3. Completion and Discontinuation of Subjects**

Subjects will be considered to have completed the study if they complete all visits up to and including Visit 9 (EOS).

Subjects who are randomized and dosed with SM, but who withdraw or are withdrawn from participation in the study by the Investigator prior to study completion (Week 20, Day 140), are instructed to return to the study site for an early termination (ET) visit within 1 week after discontinuation of SM. Procedures listed for Visit 9 (EOS) should be completed at the ET visit.

Subjects who exit the study early are required to gradually discontinue their SM over a period of up to 3 weeks by reducing their daily dose by one capsule every week until subjects are no longer taking the SM. The subject will return to the clinic for the EOS assessments within 1 week after discontinuation of SM. The final safety assessment will be conducted via telephone contact 1 to 3 weeks after the ET/EOS visit.

The reason for early termination will be recorded in the case report form (eCRF).

The Investigator(s) or subjects/caregivers may stop SM treatment at any time for safety or personal reasons. The subject's caregiver is free to withdraw their child from the study at any time for any reason without prejudice to their future medical care by the physician or at the institution. The Sponsor may also withdraw the subject at any time in the interest of subject safety. The withdrawal of a subject from the study should be discussed where possible with the Medical Monitor and/or Clinical Research Associate (CRA) before the subject discontinues taking SM. Subjects removed from the study for any reason will not be replaced.

Reasons for subject discontinuation may include:

- Withdrawal of consent and assent
- Non-compliance with study procedures
- Lack of efficacy
- Investigator decision
- Occurrence of unmanageable AEs
- Lost to follow-up
- Other

The primary reason for subject discontinuation will be recorded in the electronic case report form (eCRF). If a subject is withdrawn for more than one reason, each reason should be documented and the most medically significant reason should be entered on the eCRF.

If a subject misses any doses of SM during this study, the Investigator shall counsel the subject's caregiver on the importance of adherence. If the subject has consistently missed doses, he or she may be discontinued from the study at the discretion of the Investigator and in consultation with the Medical Monitor and the Sponsor; all procedures for discontinuation will be followed.

Efforts will be made by the study site staff to discuss with the parents/caregivers the meaning of adherence on the completion of the daily diary as at least 70% compliance with the migraine diary is requested.

### **3.4. Study Treatments**

#### **3.4.1. Study Medication Identity, Packaging, and Labeling**

SPN-538 consists of a three-pellet composite formulation containing one enhanced immediate-release pellet type contributing 6% of the label claim, and two extended-release pellet types contributing 10% and 84% of the label claim, respectively. The drug product contains the same active pharmaceutical ingredient, TPM, as the marketed IR product Topamax.

[figure not shown]
SPN-538 25-mg capsules will be used for the study. Placebo capsules will be identical in appearance to the SPN-538 capsules but contain no TPM. Study medication (active and matching placebo capsules) will be supplied in 100-count bottles. All SM bottles will be labeled by the Sponsor in a double-blind configuration and numbered according to the randomized assignment.

### **3.4.2. Study Medication Administration**

Study medication will be administered as a single oral dose QD with or without food, at bedtime. The capsules must be swallowed whole and intact and must not be sprinkled on food, crushed, chewed, cut or dissolved before swallowing. Subjects will take the first dose at the clinical site at Visit 3 (Day 1) and continue the day after with administration at bedtime.

### **3.4.3. Study Medication Dosing**

The dose of SM will be flexible and optimized based on individual tolerability. The recommended target daily dose will be determined by the Investigator based on the subject's body weight and fall within the range of 2 to 3 mg/kg/day. The maximum allowed daily dose will not exceed 100 mg/day (or four 25-mg capsules once daily); the minimum daily dose may not be less than 0.5 mg/kg/day. Individual dose recommendations will be calculated based on weight and tolerability as shown in the below Table.

### **3.4.4. Method of Assigning Subjects to Treatment Groups**

Eligible subjects will be randomized in a 1:1 ratio at Visit 3 to receive either SPN-538 or placebo. Randomization will be stratified by number of migraine days (high vs. low) at baseline to ensure treatment balance in each stratum. High monthly migraine stratum will be defined as 6 to 14 migraine days observed during the 28-day Prospective Baseline Period; and low monthly migraine stratum will be defined as 3 to < 6 migraine days during the 28-day Prospective Baseline Period.

- **Treatment A:** Placebo
- **Treatment B:** SPN-538

Allocation of study treatment will occur centrally via an interactive web response system (IWRS) using a randomization schedule to determine the SM assignment for each subject being randomized.

### 3.4.5. Blinding and Unblinding

Study subjects/caregivers and all personnel involved with the conduct and interpretation of the study, including the Investigators, study site personnel, the Sponsor and clinical staff, including the Medical Monitor, will be blinded to the treatment codes. Blinding will be maintained by providing capsules for placebo that are identical in appearance to the active drug. Neither the sponsor, subjects, caregivers, investigators, nor other study personnel will be aware of a subject's treatment assignment. In the event that it becomes medically necessary to identify which treatment a subject has received, the blind can be broken. The Investigator will follow the trial's randomization procedures to unblind the subject and should ensure that the code is broken only in accordance with the protocol. The Investigator will promptly document and explain to the Sponsor any premature unblinding (e.g., accidental unblinding, unblinding due to a serious adverse event) of treatment assignment.

Randomization schedule data will be kept strictly confidential, filed securely by the IWRS vendor, and accessible only to authorized persons until the time of unblinding. The IWRS manager is not required to be blinded, and he or she will have access to the study medication list and the randomization code. A limited number of Supernus personnel will perform the plasma concentration assays and interpret the results for the PK analysis and will be aware of the plasma concentration data during the study. These personnel will not have access to the randomization schedule, will not be associated with the clinical conduct of the study, and will not reveal to any clinical personnel involved in the study the treatment to which a subject is assigned.

### 3.5. Sample Size and Power Considerations

Based on data from previous studies conducted in adolescents and adults (MIGR-001, MIGR-002 and MIGR-003), a common SD of 3 is assumed for both the treatment and control group. Assuming a treatment difference of 1.1, a sample size of 117 subjects per arm (a total of 234 subjects) will yield 80% power to detect a non-zero difference in the mean change from baseline in the monthly migraine days between the SPN-538 and the placebo groups using a two-sample t-test at a 2-sided significance level of alpha=0.05.

Assuming that approximately 15% of subjects will drop-out before completing the study, a total sample size of 276 subjects (138 subjects per arm) will be randomized in the study.

## 4. Definitions and Derivations

- 1) Baseline: Unless specified otherwise, baseline is defined as the non-missing value collected most recent to and before the time of the very first dose of the SM.
- 2) The 28-day rate for the prospective baseline = (total number of migraine days during the last 4 weeks prior to randomization/ total number of days prior to randomization) \*28.
- 3) Headache Day is any calendar day in which the subject experiences one of the following: a qualified migraine headache, a non-migraine headache that lasts continuously for more than 30 minutes, or a headache of any duration for which acute medication was used.
- 4) Severity of Headache is rated on a scale of 0-10: 0=None, 1- 3=Mild, 4-6=Moderate, 7-9=Severe, 10=Very severe.
- 5) Migraine is defined as any headache with or without aura that meets **both A and B**

**criteria** as described below (with matched question #s in 538P401 Protocol Appendix 2 Headache Diary).

**A Criteria:**

At least **one** of the following:

- 1) Headache duration  $\geq 30$  minutes with pain medication(s):

*Questions #2 & #3: duration  $\geq 30$  min*

*Question #4 checked any of the boxes or Question #14 checked yes*

- 2) Headache duration  $\geq 60$  minutes with or without pain medication(s):

*Questions #2 & #3: duration  $\geq 60$  min*

**B Criteria:**

At least **two** of the following:

- 1) Unilateral location:

*Question #7 checked with either Right or Left.*

- 2) Pulsatile quality:

*Question #6 checked with at least one of (throbbing, pounding, stabbing, constant, sharp, pressure, pulsating with the heartbeat, squeezing or other).*

- 3) At least moderate pain intensity:

*Question #5b rated  $\geq 4$  in the pain scale*

- 4) Aggravation by physical activity:

*Question #11 checked yes*

- 6) Headache/Migraine Duration is defined as the difference between the headache end date time minus start date time.
- 7) Change from Baseline = value at current time point – value at baseline.
- 8) Treatment Emergent Adverse Event (TEAE) = any adverse event with an onset date/time after first dose of study medication.
- 9) Duration of Adverse Event = AE end date – AE start date + 1
- 10) Duration of Treatment Exposure = date of last dose – date of first dose + 1
- 11) Percent of Study Medication Compliance is calculated as

$\% \text{ compliance} = 100 * (\text{Num}/\text{Den})$ , where

$$\text{Num} = \sum_{i=3}^7 \# \text{ of capsules dispensed at } \text{visit}_i - \# \text{ of capsules returned at } \text{visit}_{i+1}$$

$$\text{Den} = \sum_{i=3}^7 x_i \times (\# \text{ of days between } \text{visit}_i \text{ and } \text{visit}_{i+1}), \text{ where}$$

$x_i = \# \text{ of capsules per day assigned to be administered at } \text{visit}_i$

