10 APPENDICES

10.1 Study Definitions and ICHD-3 Diagnostic Criteria

Study Definitions

ICHD-3 outlines special features that are characteristic of migraine headaches in children and adolescents (aged under 18 years), including the following:

- In children and adolescents, migraine attacks may last 2-72 hours.
- In children and adolescents, migraine headache is often bilateral; unilateral pain usually emerges in late adolescence or early adult life.
- In children and adolescents, aura may be represented by less typical bilateral visual symptoms.
- In children, migraine headache is usually frontotemporal. Occipital headache is rare and calls for diagnostic caution.
- In young children, photophobia and phonophobia may be inferred from their behavior.

Migraine episode is defined as the occurrence of any migraine that starts, ends or recurs within a 24-hour period. Migraine episodes that persist or recur within a 24-hour period are considered the same episode.

Monthly migraine is measured by the number of migraine days within 28 days. A migraine day is defined as a calendar day (12:00 am to 11:59 pm) in which the subject experiences a migraine attack that starts, ends or recurs within 24 hours and lasts for \geq 1 hour (if untreated) or \geq 30 minutes (if interrupted with rescue medication). Pain persisting for more than 1 calendar day (\geq 24 hours) after initial onset will be considered as a new, distinct headache day.

Headache Day is any calendar day in which the subject experiences one of the following: a qualified migraine headache, a non-migraine headache that lasts continuously for more than 30 minutes, or a headache of any duration for which acute medication was used.

ICHD-3 Diagnostic Criteria

Per the IHS Criteria for Classification of Migraines in Children and Adolescents (aged less than 18 years) (<https://www.ichd-3.org/>; *Headache Classification Committee of the International Headache (IHS), Cephalalgia, 2018, 38 (1): 1-211*).

Migraine Without Aura

Previously used terms:

Common migraine; hemicrania simplex.

Description:

Recurrent headache disorder manifesting in attacks lasting 4-72 hours. Typical characteristics of the headache are unilateral location, pulsating quality, moderate or severe intensity, aggravation by routine physical activity and association with nausea and/or photophobia and phonophobia.

Diagnostic criteria:

- A. At least five attacks ^{Note #1} fulfilling criteria B-D

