- B. Headache attacks lasting 4-72 h (untreated or unsuccessfully treated) ^{Notes #2; #3}
- C. Headache has at least two of the following four characteristics:
 - unilateral location
 - pulsating quality
 - moderate or severe pain intensity
 - aggravation by or causing avoidance of routine physical activity (e.g., walking or climbing stairs)
- D. During headache at least one of the following:
 - nausea and/or vomiting
 - photophobia and phonophobia
- E. Not better accounted for by another ICHD-3 diagnosis.

Notes:

1. One or a few migraine attacks may be difficult to distinguish from symptomatic migraine-like attacks. Furthermore, the nature of a single or a few attacks may be difficult to understand. Therefore, at least five attacks are required. Individuals who otherwise meet criteria for 1.1 *Migraine without aura* but have had fewer than five attacks should be coded 1.5.1 *Probable migraine without aura*.
2. When the patient falls asleep during migraine and wakes up without it, duration of the attack is reckoned until the time of awakening.
3. In children and adolescents (aged under 18 years), attacks may last 2-72 hours (the evidence for untreated durations of less than two hours in children has not been substantiated).

Migraine With Aura

Previously used terms:

Classic or classical migraine; ophthalmic, hemiparaesthetic, hemiplegic or aphasic migraine; migraine accompagnée; complicated migraine.

Description:

Recurrent attacks, lasting minutes, of unilateral fully reversible visual, sensory or other CNS symptoms that usually develop gradually and are usually followed by headache and associated migraine symptoms.

Diagnostic criteria:

- A. At least two attacks fulfilling criteria B and C
- B. One or more of the following fully reversible aura symptoms:
 - visual
 - sensory
 - speech and/or language
 - motor
 - brainstem
 - retinal
- C. At least three of the following six characteristics:
 - at least one aura symptom spreads gradually over ≥ 5 minutes
 - two or more aura symptoms occur in succession
 - each individual aura symptom lasts 5-60 minutes ^{Note #1}
 - at least one aura symptom is unilateral ^{Note #2}
 - at least one aura symptom is positive ^{Note #3}
 - the aura is accompanied, or followed within 60 minutes, by headache
- D. Not better accounted for by another ICHD-3 diagnosis.

Notes:

1. When for example three symptoms occur during an aura, the acceptable maximal duration is 3×60 minutes. Motor symptoms may last up to 72 hours.

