10.2 Headache Diary – Preventive Therapies (Version 2.0)

Instructions: This form should be completed by the participant for each day the participant/subject experienced a headache/migraine.

1. Did you experience a headache today? Yes No
2. What time did your headache start? (24 hour clock) Woke up with this headache
3. What time did your headache end? (24 hour clock) Headache resolved after falling asleep
4. What acute pain medication(s), in addition to the study drug, did you take? (Choose all that apply)

 Acetaminophen	 Ibuprofen
 Almotriptan	 Naproxen
 Aspirin	 Naratriptan
 Dihydroergotamine (DHE)	 Rizatriptan
 Eletriptan	 Sumatriptan
 Ergotamine tartrate (ET)	 Zolmitriptan
 Frovatriptan	 Other, specify:
5. Describe the worst severity of your headache today? Complete one of the following pain severity scales:
 - a. Which word describes the severity of your headache?
 None Mild Moderate Severe Very Severe (for cluster headaches)
 - b. Rate your overall worst pain for this headache on a scale of 0-10: ("0" = no pain & "10" = the worst pain): 0 1 2 3 4 5 6 7 8 9 10
6. Do any of the following describe your pain? (Choose all that apply)

 Throbbing	 Pressure
 Pounding	 Pulsating with the heart beat
 Stabbing	 Squeezing
 Constant	 Other, specify:
 Sharp	
7. Where is the location of your headache pain? (Choose one)
 Right Left Bilateral (both sides)
8. Where is the location of your headache pain that hurts the most? (Choose all that apply)

 Top	 All over
 One Eye (specify,  left  right)	 Right Temple
 Around Eyes	 Left Temple
 Behind Eyes	 Front
 Back	 Other, specify:
 Neck	

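### SAP migraine criterion B2, labelled pulsatile quality, accepts every option of diary Question 6, so it cannot discriminate once that question is answered

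*SAP*

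**What the plan says.** SAP section 4, item 5 classifies each headache from the diary answers. Criterion A is duration: 30 minutes or more if pain medication was taken, or 60 minutes or more regardless. Criterion B needs two or more of four features: unilateral (Question 7), pulsatile (Question 6), pain of at least 4 (Question 5b) and aggravation by activity (Question 11). The pulsatile feature, B2, is met by "Question #6 checked with at least one of (throbbing, pounding, stabbing, constant, sharp, pressure, pulsating with the heartbeat, squeezing or other".

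On the form in protocol Appendix 10.2, Question 6 asks "Do any of the following describe your pain? (Choose all that apply" and offers nine boxes. They are the same nine as in the SAP list; there is no tenth.

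The intensity cut-off follows SAP section 4, item 4: "Severity of Headache is rated on a scale of 0-10: 0=None, 1- 3=Mild, 4-6=Moderate, 7-9=Severe, 10=Very severe". A score of 4 is therefore the lowest moderate value.

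For comparison, ICHD-3 criterion C in protocol Appendix 10.1 reads "Headache has at least two of the following four characteristics", one of the four being "pulsating quality". Criterion D then adds associated symptoms: "During headache at least one of the following".

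SAP 5.1 puts days of migraine in the numerator of the 28-day rate, both for the last four weeks of treatment and for the prospective baseline. The responder endpoint in SAP 5.2 uses the same count.

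**The concern.** A criterion that every possible answer satisfies does no work. B2's label says it tests for pulsatile pain, but its list also takes *pressure*, *squeezing*, *constant* and *other*. With B2 met by default, the requirement for two features drops to one of the remaining three.

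What is at stake is whether the primary endpoint measures what its name says. The protocol treats the distinction as material: subjects who cannot tell migraine from other headaches are excluded (exclusion 1), and total headache days are a separate secondary endpoint. A looser migraine rule brings the two counts closer together.

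**Working it through.** The plan gives no figure for this point, so the check is by enumeration.

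**Step 1: can an answered Question 6 fail B2?** Nine boxes, any number ticked, at least one: 2^9 − 1 = 511 possible answers. All 511 contain a listed descriptor, so all 511 meet B2. A blank Question 6 does not.

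**Step 2: what criterion B becomes.** Write U for unilateral, P for a genuinely pulsatile description, I for pain ≥4 and A for aggravation by activity, each 0 or 1.

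- SAP rule with Question 6 answered: 1 + U + I + A ≥ 2, that is U + I + A ≥ 1.
- Rule implied by the label (and criterion C): U + P + I + A ≥ 2.

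| Patterns considered | Qualify under SAP rule | Qualify if B2 meant pulsatile |
|---|---|---|
| All 16 | 14 | 11 |
| Non-pulsatile (8) | 7 | 4 |
| Bilateral (8) | 6 | 4 |
| Bilateral and non-pulsatile (4) | 3 | 1 |
| Pain ≥4 (8) | 8 | 7 |

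The rules differ in 14 − 11 = 3 patterns: (U,P,I,A) = (1,0,0,0), (0,0,1,0) and (0,0,0,1). These are the headaches with no pulsatile descriptor and exactly one other feature. The two patterns that still fail the SAP rule have U = I = A = 0: mild, not one-sided and not worsened by activity.

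**Step 3: a worked case.** Bilateral, *pressure* ticked, pain 4, 60 minutes, not worsened by activity. A is met by duration, B2 by the tick and B3 by the score, so it is a migraine. Under the label's meaning it has one feature (I = 1) and does not qualify.

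**Step 4: a narrower B2.** No passage says which descriptors are pulsatile, so this is an assumption shown as a range.

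- Throbbing, pounding or pulsating: six boxes are left that do not count, so 2^6 − 1 = 63 of the 511 answers fail and 511 − 63 = 448 pass.
- Pulsating only: 2^8 = 256 of the 511 pass.
- For the bilateral headache in Step 3 with a single box ticked, qualifying answers fall from 9 of 9 to 3 of 9 or 1 of 9.

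These counts weight every pattern equally. They describe the rule and are not estimates of how often such headaches occur.

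**The case against.** **Criterion C is not the protocol's rule for counting days.** It belongs to the diagnosis of the disorder, which subjects meet at entry. The migraine-day definition in protocol 2.5 lists neither C nor D, and SAP criterion A takes its durations from there, not from Appendix 10.1. This stands in part. The SAP rule already departs from ICHD-3 on duration and associated symptoms, so a reader should not infer that narrowing B2 would restore ICHD-3. Criterion C, which protocol 6.1 invokes for the diary, supports B2's label; the firm defect is that label and list disagree.

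**Caregivers may screen first.** One sentence of protocol 6.1 can be read as having the detailed diary completed only for headaches already judged to be migraine by ICHD-3. But 6.1 also asks for details on any headache day, protocol 3.1 records symptoms of all headaches, the form says "This form should be completed by the participant for each day the participant/subject experienced a headache/migraine", and the SAP applies its rule to any headache. Non-migraine headaches can reach the rule; how many do is not stated.

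**A broad list may suit ages 6 to 11.** Young children may not describe pulsation well, and Appendix 10.1 notes "In children and adolescents, migraine headache is often bilateral". This is a fair reason to accept more descriptors, but the available text does not give it.

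**No harm is shown.** A reader might infer bias in favour of the drug, or a quantified loss of power through dilution. The documents support neither. The rule is identical in both arms and at baseline. A power loss would need the share of counted days that are not migraine and their response to treatment; the documents give neither, and total headache days are themselves an efficacy objective.

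**The pattern counts assume complete answers.** Question 6 can be left blank. The form also asks for one of 5a or 5b while B3 reads only 5b, although protocol 6.1 specifies the 0 to 10 scale. Correct, and the claim is limited accordingly.

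**Conclusion.** The point holds as a mismatch between B2's label and its list, inside the definition that feeds the primary endpoint, its baseline and the responder endpoint. Confidence is high on the wording: with Question 6 answered, B2 is always met and criterion B reduces to one feature of three. The size is 14 qualifying patterns against 11, with the difference confined to non-pulsatile headaches having exactly one other feature. For headaches of pain ≥4 the rules differ in one pattern of eight.

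Impact on the trial is undetermined. The number of non-migraine headaches counted, and any effect on the estimate or power, cannot be obtained from the documents. The two sensitivity analyses named in protocol 7.8.1 both concern missing data. SAP 7.1 is not in the public copy, so nothing is inferred about an alternative definition there. The matter should be settled before unblinding, when the choice cannot be influenced by results.

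**What to change.** Before unblinding, in SAP section 4, item 5:

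- State which Question 6 descriptors count as pulsatile, and why.
- Prespecify a sensitivity analysis that repeats the primary and responder analyses with B2 limited to those descriptors (for example throbbing, pounding and pulsating), unless SAP text outside the public copy already does this.
- Apply the narrower rule alike to baseline and treatment periods, and keep all subjects in the arm and stratum as randomised. State how responder status is set if the recount leaves a subject with no baseline migraine days.
- If the sponsor confirms that the nine-item list was not intended, correct B2 in the primary definition instead.

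The sensitivity analysis comes first because changing the primary definition is a trade-off. Counted migraine days would fall, some subjects could drop below 3 baseline migraine days or cross the stratum boundary on recount, and some true attacks described only in non-pulsatile words would be lost. That loss is limited to attacks with exactly one of the other three features, but it may not be trivial where bilateral migraine is common.

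The cost is a SAP edit and a little extra programming on data already collected.
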